### **6.8. Weight**

Body weight will be measured at all visits, without heavy outer clothing or footwear.

### **6.9. ECG**

A standard 12-lead ECG will be performed on all subjects at baseline and visit 4.

### **6.10. Laboratory Samples**

All subjects will be required to fast for a minimum of 12 hours prior to collection of each blood sampling. Any subject diagnosed with DS and lacking a karyotype-proven diagnosis will undergo blood draws for this test on visit 1.

During Visit 2 & 3 blood samples will be collected after study dose administration and prior to memory and cognitive testing.

## **7. INVESTIGATIONAL PRODUCTS**

### **7.1. Description of Investigational Products**

The Research Center will utilize the following investigation products:

- Insulin glulisine
- Placebo saline
- POD Device
- Syringe

### **7.2. Handling and Storage**

The study drug must be handled and/or administered only by an authorized investigative staff member.

The study drug will be kept per label recommendations and institutional Standard Operational Policy, specifically, but not limited to temperature controlled secure area.

### **7.3. Treatment Assignment**

Randomization will be stratified by gender *a priori* by the permuted block method. Sequences will be assigned for each gender by random selection of one of the twenty permutations of block of size 6 such that 3 of each gender are allocated to group 1, and 3 of each gender are allocated to group 2. The trial is a double blinded study so that neither the subject, the investigator, nor the trial coordinator will know to which sequence the subject has been randomized. To facilitate subject blinding, all subjects will undergo the same follow-up procedures. One clinician at the site will be unblinded to randomization and prepare the study dose for each subject. This person will not have responsibility for obtaining any study data. The investigators will be provided

with a sealed envelope containing the true sequence of glulisine and saline for each group if the blind needs to be broken due to unforeseen circumstances.

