### **4. STUDY DESIGN**

This study is a single center, randomized, double-blind, placebo-controlled, cross-over pilot study designed to assess the safety of IN glulisine versus placebo in patients with DS.

After written informed consent has been obtained from the subject and their caregiver, subjects will be screened to assess study eligibility based on the study inclusion/exclusion criteria.

A total of twelve subjects (n=12) will be randomized in this cross-over study and within subject comparisons conducted between single treatment of IN glulisine and placebo. All subjects will receive a single test treatment of placebo prior to randomization to ensure adherence to study procedures. Twenty minutes after receiving IN treatment, DS subjects will undergo cognitive testing with Fuld Object Memory Evaluation and Story Recall subtest of the Rivermead Behavioral Memory Test for Children.

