### **6.3. Early Withdrawal**

If subject withdraws from the study after the screening visit, no further evaluations are necessary. If subject withdraws from the study after visit 2, all safety assessments will be performed (see section 6.2.4.) and the investigators will be unblinded. For specific laboratory assessments refer to Table 1 Laboratory Assessments (see section 6.10.).

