### **11.5. Provision of Study Results and Information to Investigators**

Study results will be made available by the study statistician once analysis (Interim Analysis) is complete. Study Staff will not be unblinded in regards to individual subjects randomization status until after the database is locked.

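### The only emergency code in section 7.3 is one envelope keyed to group, and no written procedure confines a code break to one subject

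*Combined protocol and SAP*

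**What the plan says.** Section 7.3 (Treatment Assignment) randomizes subjects to group 1 or group 2, stratified by gender. It states that "neither the subject, the investigator, nor the trial coordinator will know to which sequence the subject has been randomized". It then supplies one tool for breaking the blind, held by the investigators: a "sealed envelope containing the true sequence of glulisine and saline for each group", to be used in unforeseen circumstances. The envelope is singular and its content is keyed to group.

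The same section leaves one clinician at the site unblinded, to prepare the doses and with no part in collecting data. It gives that person no role in a code break. It does not say whether the investigators or the coordinator can see which group number a subject carries. The label contents listed in section 7.4 include neither a group number nor a subject number.

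Two other sections bear on unblinding. Section 6.3, on withdrawal after Visit 2, requires the final safety assessments "and the investigators will be unblinded". Section 11.5 says that "Study Staff will not be unblinded in regards to individual subjects randomization status until after the database is locked".

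**The concern.** In a two-sequence crossover, the meaning of the two group codes plus a list of who is in which group is the entire randomization key. A code break should answer one question about one subject. A group-level envelope either answers it for everyone whose group label is known, or answers it for no one until somebody supplies the label.

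What is at stake is the blinding of the primary endpoint. Section 3.3 counts any or related adverse events. Sections 9.1 and 9.2.1 make the investigator's view of clinical significance part of deciding whether an abnormal finding counts as an adverse event. An investigator who knows a subject's sequence knows which visit was glulisine and which was saline, and that is the contrast the within-subject analysis estimates. In a single-center study of 12, the people judging the remaining subjects are likely to be the same few.

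**Working it through.** **Inputs**
- Randomized: 12 (section 4: "A total of twelve subjects (n=12) will be randomized in this cross-over study").
- Allocation: "random selection of one of the twenty permutations of block of size 6", giving 3 subjects per group within each gender (section 7.3).
- Treatment periods: 2 per subject, one glulisine and one placebo (section 4), so 12 × 2 = 24 in all.
- Replacements: withdrawals are to be replaced to keep 12 (section 8.2), so more than 12 may be randomized.
- Visibility of group labels to blinded staff: not stated. Both cases are worked below.

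**The plan's own figure.** A block of 6 with 3 per group has 6!/(3! × 3!) = 720/36 = 20 arrangements, as section 7.3 says. Two genders × 6 = 12 subjects, with 3 + 3 = 6 in each group.

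**What one opening decodes under section 7.3 as written**

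| Situation | Subjects decoded | Periods decoded |
|---|---|---|
| Labels visible, all 12 randomized | 6 + 6 = 12 of 12 | 24 of 24 |
| Labels visible, k randomized so far | k, then each later or replacement subject once labelled | 2k, then 2 for each subject added |
| Labels hidden, envelope alone | 0 of 12 | 0 of 24 |
| Labels hidden, unblinded clinician discloses one subject's group (not written in the protocol) | 1 of 12 | 2 of 24 |

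**Subject-level envelopes alone are not enough.** Suppose labels stay visible and one subject in group 1 is shown to have had glulisine first. Every other group 1 subject is then decoded and, by elimination, so is group 2. Masking the label is the essential step.

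**What remains after the change.** With labels masked and one subject decoded, 1 of 12 subjects (2 of 24 periods) is known exactly. Someone who also knows the block size can infer a little more. Of the 20 arrangements, 10 are compatible with the revealed subject. The other five places of that gender's block then hold 2 of the same sequence and 3 of the opposite one, so the best guess for each is right with probability 3/5 = 0.60. For the six subjects of the other gender it stays at 3/6 = 0.50.

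**Sections 6.3 and 11.5 side by side.** Section 6.3 plans unblinding of the investigators when a subject withdraws after Visit 2. Section 11.5 allows no individual unblinding of study staff before database lock. For a subject who withdraws before lock, both cannot be followed, whatever form the code takes.

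**The case against.** The strongest defence is that section 7.3 already contains a way to limit a break. The unblinded clinician knows every assignment and, with labels hidden, could disclose just one. This stands as far as it goes. A reader might infer that every break must either expose the whole trial or fail, and the documents do not support that. But the clinician's part in a break is unwritten, and so is that person's availability, so the defence shows an incomplete procedure rather than a sound one.

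A reader might also infer that any opening compromises all 12 subjects and 24 periods. That needs visible labels and full accrual, and the protocol states neither as the situation at a break. Decoded periods are also not the same as compromised assessments: the later the break, the more judgements have already been recorded blind.

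Nor can the documents say how often a break would happen. If each of 12 subjects had an assumed 5%, 10% or 15% chance of triggering an opening, 1 − (1 − p)^12 would give 46%, 72% or 86% for at least one. These are illustrations only. The protocol gives no withdrawal rate, section 6.3 does not say that the envelope is the means of unblinding, and section 7.3 reserves it for the unforeseen. The placebo test dose before randomization and the short gaps between visits may also keep withdrawals few. What does stand is that section 6.3 makes some unblinding before the end of the trial foreseeable.

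Finally, it is tempting to rest the bias argument on relatedness, but no section says who judges it. The argument needs only clinical significance, which is expressly the investigator's.

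**Conclusion.** The point holds in a limited form. The only written code-break tool is keyed to group, and nothing written confines a break to one subject.

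- If investigators can see group labels, one opening ends blinding for all later judgements on everyone randomized so far and on each subject added afterwards. The worst case is 12 of 12 subjects.
- If they cannot, the envelope by itself decodes 0 of 12 and does not serve its purpose without an unassigned helper.

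Which case applies is not stated, so the 12 of 12 is an upper bound and not an expected loss. Assessments recorded before a break are unaffected. Sample size, power and alpha do not change. The section should be changed because the remedy costs so little against a possible loss of blinding in a trial this small. The conflict between sections 6.3 and 11.5 is a separate matter that this change does not settle.

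**What to change.** In section 7.3:

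1. State that group labels are masked from the investigators and the coordinator, and that the group key stays with the unblinded clinician and the holder of the randomization list.
2. Replace the group-level envelope with individually numbered, opaque, sealed codes, one for each randomized or replacement subject, each holding only that subject's sequence.
3. Require that one code is opened per break, and that each opening is logged.

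A logged disclosure of a single subject's sequence by the unblinded clinician would contain a break equally well, provided labels are masked and the role is written down.

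The cost is a short protocol edit and about 12 to 20 envelopes, with no added staff, visits or subjects. The limited block-based inference shown above would remain.

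Separately, reconcile sections 6.3 and 11.5 so that they agree on whether, and for whom, unblinding may occur before database lock.

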#### **7.4. Packaging and Labeling**

All study drug and placebo will be labeled according to the following specifications:

- IRB number
- Quantity statement
- Directions – To be administered only by investigative study staff
- Storage conditions per label
- “For Clinical Trial Use Only”

#### **7.5. Occupational Safety**

No known significant safety risks exist to site personnel in direct or indirect contact with the study drug.

### **8. SUBJECT COMPLETION AND WITHDRAWAL**

#### **8.1. Subject Completion**

Subjects completing all 4 study visits will be considered to have completed study.

#### **8.2. Subject Withdrawal**

Subject may withdraw from study at any time for any reason without penalty or be terminated from the study by the clinical investigator (see provisions for termination by study team.) Investigational team will document the reason(s) for withdrawal. In the event a subject chooses to withdraw from study before Visit 4 the safety procedures described in Section 6.2.4. and will be performed ideally within 14 days following subject's decision to withdraw. For all subjects who withdraw, all final safety assessments will be collected regardless of time elapsed since previous visit. In addition to final visit, subjects who withdraw early will be contacted within 7 days by study staff via telephone to assess development of new and/or ongoing AEs and concomitant medications. Efforts will be made to recruit subjects to replace any withdrawals so as to maintain an n=12.

Subject's participation may be terminated at the discretion of the investigator. Individuals may be withdrawn for the following reasons:

- Clinically significant adverse events
- Lost to follow-up
- Protocol violations
- Inability to tolerate study medication
- Other

## **9. ADVERSE EVENTS (AE) AND SERIOUS ADVERSE EVENTS (SAE)**

### **9.1. Definition of AE**

An adverse event is any symptom, sign, illness or experience which develops or worsens in severity during the course of the study. Interval development of illnesses or injuries will be regarded as adverse events. Abnormal results of diagnostic procedures are considered to be adverse events if the abnormality:

- Results in study withdrawal
- Is associated with clinical signs or symptoms
- Leads to treatment or to further diagnostic tests
- Is considered by the investigator to be of clinical significance

### **9.2. Definition of SAE**

Adverse events are classified as either serious or non-serious. A serious adverse event is any event that results in:

- Death
- Life-threatening situation
- Hospitalization or prolongation of hospitalization
- Disability or incapacitation
- Other events determined by investigator to be medically significant in which subject's well-being is jeopardized (e.g. events that have high likelihood of escalating to the point of meeting criteria outlined above)

#### **9.2.1. Clinical Laboratory Abnormalities and Other Abnormal Assessments as AEs and SAEs**

Any new abnormal, vital, examination, or laboratory finding judged clinically significant by the investigator will be documented as an AE or SAE, if meeting the definitions for such. Abnormal lab findings or other abnormal assessments associated with the disease under study will not be considered AEs or SAEs unless more severe than expected, as judged by the investigator.

#### **9.2.2. Time Period and Frequency of Detecting AEs and SAEs**

Upon consenting, a subject is considered to be a participant in the study, and until that person either withdraws or completes study, AEs and SAEs will be recorded. The investigational team will promptly report any AE/SAE as required per federal guidelines.

## **10. DATA ANALYSIS AND STATISTICAL CONSIDERATIONS**

### **10.1. Statistical Analysis**

All primary and secondary endpoints will be summarized within strata defined by treatment and study period.

Treatment effects on both primary and secondary endpoints will be assessed using common statistical methodology for crossover trials. Continuous outcomes, such as the FOME and the RBMT-C, and count outcomes, such as adverse event incidence, will be analyzed using a mixed-effects linear model to account for period effects and patient characteristics such as age and sex. Plots of the observed effects will be constructed to aid with interpretation.

All statistical analyses will be completed using SAS® software. Visual representations of the data will be constructed using the package ‘ggplot2’ in R [63, 64].

## **10.2. Safety Outcomes**

The primary endpoint is defined as the ‘incidence of any or related adverse and/or serious events of intranasal glulisine versus placebo.’ The difference in incidence of adverse events between subjects receiving glulisine and those receiving saline will be modeled in terms of rates using a mixed-effects Poisson regression model accounting for period and the treatment-period interaction as well as subject age and sex.

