#### **3.3. Primary Endpoint**

Incidence of any or related adverse and/or serious events of intranasal glulisine versus placebo.

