### **6.4. Safety**

For all safety assessment described below, any clinically significant change will be recorded as an AE or SAE.

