## **10.4. Study Power**

Power analysis for the primary endpoint (incidence of adverse events) is simplified to a comparison of paired means. The following table presents power estimates for a variety of assumptions. Assumptions common to all scenarios are a sample size of 12 and an alpha of 0.05. The difference column corresponds to the difference in number of adverse events between the treatment and the placebo. Although only half of these probable scenarios are adequately powered, such a result is acceptable for a pilot study such as this.

| Difference | St. Dev. | Power |
|-------------------|-----------------|--------------|
| 1.5               | 1.0             | 0.997        |
| 1.5               | 1.5             | 0.883        |
| 1.5               | 2.0             | 0.658        |
| 2.0               | 1.0             | 1.000        |
| 2.0               | 1.5             | 0.987        |
| 2.0               | 2.0             | 0.883        |

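### Sections 10.1 and 10.2 name different models for the primary adverse event counts, and the Poisson model in 10.2 makes no provision for dispersion or sparse counts

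*Combined protocol and SAP*

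**What the plan says.** The primary endpoint in Section 3.3 is "Incidence of any or related adverse and/or serious events of intranasal glulisine versus placebo". Two sections of the analysis plan assign it a model:

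- Section 10.1: "count outcomes, such as adverse event incidence, will be analyzed using a mixed-effects linear model to account for period effects". A linear mixed model estimates a residual variance.
- Section 10.2: the difference "will be modeled in terms of rates using a mixed-effects Poisson regression model accounting for period and the treatment-period interaction", with age and sex as covariates. No scale parameter, robust standard error, exact method or type of test (Wald or likelihood ratio) is named.

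Section 10.4 takes a third route: "Power analysis for the primary endpoint (incidence of adverse events) is simplified to a comparison of paired means". It sets the standard deviation separately from the difference.

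The counting unit is broad. Section 9.1: "An adverse event is any symptom, sign, illness or experience which develops or worsens in severity during the course of the study". Section 6.4: "For all safety assessment described below, any clinically significant change will be recorded as an AE or SAE". No rule says when linked findings from one dose are merged into one AE. Some findings can occur only once per dose: Section 6.7 has a single post-dose fingerstick glucose, and it calls any change above 10% clinically significant.

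**The concern.** In a two-period crossover the treatment contrast is within-subject. A random subject intercept estimates how much subjects differ from one another. It does not absorb clustering or regularity of events inside one subject-period, where a Poisson model without a dispersion term holds the variance at the mean.

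The plan's recording rules allow departures both ways. If one reaction is recorded as two or three AEs, the variance exceeds the mean and the standard error is too small. If a reaction can occur only once per dose, the variance is below the mean and the standard error is too large. A safety comparison could then flag a difference because of how AEs were split, or miss a real one. Because 10.1 and 10.2 disagree, the plan does not settle whether this applies.

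**Working it through.** **1. The plan's power table.** Inputs from Section 10.4: n = 12, alpha 0.05, differences 1.5 and 2.0, SDs 1.0, 1.5 and 2.0. Taking the SD as that of the paired difference, use a two-sided paired t-test with 11 df and noncentrality (difference/SD) × √12:

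| Difference | SD | Noncentrality | Power | Stated |
|---|---|---|---|---|
| 1.5 | 1.0 | 5.196 | 0.997 | 0.997 |
| 1.5 | 1.5 | 3.464 | 0.883 | 0.883 |
| 1.5 | 2.0 | 2.598 | 0.658 | 0.658 |
| 2.0 | 1.0 | 6.928 | 1.000 | 1.000 |
| 2.0 | 1.5 | 4.619 | 0.987 | 0.987 |
| 2.0 | 2.0 | 3.464 | 0.883 | 0.883 |

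All six reproduce. A one-sided test does not fit (0.945 and 0.785 for rows 2 and 3).

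**2. Is the table compatible with 10.2?** If counts are independent Poisson given the subject, Var(G − P) = μG + μP, which is at least μG − μP. Variation between subjects only adds to it. The SD must therefore be at least √1.5 = 1.22 for a difference of 1.5 and √2.0 = 1.41 for 2.0. Both SD 1.0 rows are impossible under the 10.2 model.

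**3. The 10.2 test.** With treatment, period and their interaction, and AE totals a, b (glulisine, saline in one sequence) and c, d (the same in the other), the period-averaged log rate ratio is ½[log(a/b) + log(c/d)]. Its standard error is ½√(1/a + 1/b + 1/c + 1/d). One full random-intercept fit with age and sex gave the same values (−0.2027, SE 0.1995). The standard error uses totals only, so the observed scatter never enters.

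**4. Clustered AEs, no treatment effect.** If the variance is φ times the mean, a nominal 5% Wald test rejects in roughly 2[1 − Φ(1.96/√φ)]. For K AEs per reaction, φ = E[K²]/E[K]; with K = 1 or 2 equally likely, φ = 2.5/1.5 = 1.67. Simulation used full model fits, 12 subjects, mean 2 AEs per dose on both treatments, subject-effect SD 0.4 on the log scale and 2,000 datasets per row:

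| AEs per reaction (assumed) | φ | Approximation | Wald z | Wald t, 10 df | Period-difference t-test |
|---|---|---|---|---|---|
| Always 1 (true Poisson) | 1.00 | 5.0% | 4.6% | 2.1% | 5.2% |
| 1 or 2 | 1.67 | 12.9% | 11.2% | 7.0% | 4.3% |
| Geometric, mean 1.5 | 2.00 | 16.6% | 15.4% | 10.8% | 4.2% |
| 1 to 3 | 2.33 | 19.9% | 19.5% | 13.5% | 5.0% |

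A likelihood ratio test at the same mean rejects in 18%, 29% and 39% with exactly 2, 3 or 4 AEs per reaction (closed form, 100,000 trials). At 0.5 AEs per dose the clustered Wald test is not inflated (0.3-1.0% with 2 to 4 AEs per reaction; 3.2% with 1 or 2), but the likelihood ratio test rejects in 24-36%.

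**5. At most one AE per dose.** Here φ = 1 − p; at p = 0.5 the approximation gives 2[1 − Φ(1.96/√0.5)] = 0.6%. The simulated Wald rate is lower still, because cells are sparse. Wald figures set aside datasets with an empty cell (6-22% of them); the other columns use all datasets.

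| Affected, saline v glulisine | Wald z | Likelihood ratio | Period-difference t-test |
|---|---|---|---|
| 50% v 50% (no effect) | 0.1% | 2.5% | 6.1% |
| 40% v 80% | 5.9% | 22% | 49% |
| 30% v 80% | 13.0% | 44% | 70% |

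True Poisson counts with the same means have Wald power of only 12% and 18%, so sparseness explains part of the loss.

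**6. A case by hand.** Let 12/12 subjects have one AE on glulisine and 4/12 on saline (two per sequence): a = c = 6, b = d = 2. The log ratio is log 3 = 1.099, the SE is ½√(1/6 + 1/2 + 1/6 + 1/2) = 0.577, z = 1.90 and p = 0.057. Exact McNemar on the 8 discordant subjects gives 2 × (½)⁸ = 0.008. The likelihood ratio test also rejects at 5%.

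**The case against.** The strongest reply is that Section 10.1 already sends AE counts to a linear mixed model. With complete 2×2 data its period-adjusted treatment test is essentially the t-test used above. A reader might infer that the Poisson model is the only test of the primary endpoint. The documents do not support that. What stands is a conflict: 10.2 is the specific text for this endpoint, and 10.1 does not say that it overrides it.

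A reader might also infer that the plan's test almost never detects once-per-dose reactions. That holds only for a Wald test, which the plan does not name, and part of it is sparseness and the handling of empty cells. The likelihood ratio test does better there, though it is the more inflated of the two under clustering.

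Nor is inflation of two to four times a general result. It needs about 2 AEs per dose on both treatments, including saline, and linked signs recorded separately. Section 9.1 also lists an illness as an AE, and investigator judgement may merge signs. It is likewise too strong to say that no variance is estimated, because the random intercept estimates the between-subject part.

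Pilot status, which 10.4 invokes, excuses low power. It does not excuse an error rate that depends on an unstated test and an unstated counting habit.

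**Conclusion.** The point holds in this form. Sections 10.1 and 10.2 conflict on the primary analysis, and the 10.2 model ties the within-subject variance to the mean, contrary to the free SD that 10.4 uses.

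Under assumed AE patterns, the Wald false-positive rate at about 2 AEs per dose is 11-20% when AEs cluster, or 7-14% with a t reference on 10 df. With at most one AE per dose the Wald test has about 6% and 13% power, where a t-test on period differences has about 50% and 70% and a likelihood ratio test 22% and 44%. Neither Poisson test behaves acceptably in both situations; the period-difference t-test stays near 5-6% in the null cases tabulated. The magnitudes depend on AE rates and clustering that the documents do not give. The conflict between sections and the impossible SD 1.0 rows do not.

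**What to change.** Rewrite 10.1 and 10.2 so that one primary analysis is named and it estimates the within-subject variance. Take each subject's period 1 minus period 2 AE count and compare the two sequences by a t-test on 10 df. Half the difference in sequence means is the glulisine-minus-saline difference, the quantity that 10.4 powers. A within-subject randomisation test is an acceptable alternative: a sign-flip version had size 1.2-2.7% in the clustered and 0/1 cases, with 71% power for 20% v 80% affected, against 86% for the linear analysis and 14% for Wald z. Keep the Poisson rate ratio as supportive. A scale factor alone is not enough: it controlled the clustered cases but left 14% and 22% power in the two 0/1 comparisons above.

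Cost: a short rewrite, with no extra subjects or data. If counts are truly Poisson, power for 1.25 v 2.75 AEs falls from about 74% (Wald z) to about 65%, close to the 0.658 that 10.4 accepts for difference 1.5, SD 2.0. The t-test's size with 0/1 counts is about 6%. Age and sex drop out of the within-subject contrast, where they add little. The missing rule for merging linked AEs is a separate gap that this change does not close.

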## **10.3. Cognitive Outcomes**

The secondary endpoints consist of performance differences in the FOME and the RBMT-C between subjects receiving glulisine and those receiving saline. These differences will be assessed using normal mixed-effects regression accounting for period and the treatment-period interaction as well as subject age and sex.

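### Sections 10.1 and 10.2 give the primary endpoint two different models with no order of precedence, and 10.2 and 10.3 do not say which treatment contrast is reported

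*Combined protocol and SAP*

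**What the plan says.** Section 10.1 (Statistical Analysis) states that "count outcomes, such as adverse event incidence, will be analyzed using a mixed-effects linear model", the same model as for FOME and RBMT-C, "to account for period effects and patient characteristics such as age and sex". It mentions no interaction. It also plans for all endpoints to be "summarized within strata defined by treatment and study period".

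Section 10.2 (Safety Outcomes) restates the primary endpoint and says that the difference in adverse event incidence "will be modeled in terms of rates". The glulisine-saline comparison is to be made there "using a mixed-effects Poisson regression model accounting for period and the treatment-period interaction as well as subject age and sex".

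Section 10.3 (Cognitive Outcomes) uses "normal mixed-effects regression accounting for period and the treatment-period interaction as well as subject age and sex" for FOME and RBMT-C.

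Section 10.4 (Study Power) treats the primary endpoint as "simplified to a comparison of paired means", and explains: "The difference column corresponds to the difference in number of adverse events between the treatment and the placebo". Section 4 describes the comparison of glulisine with placebo as one made within each subject.

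**The concern.** One primary endpoint has two models on two scales, with different terms, and no sentence ranks them. Section 10.2 is the more specific section. Against that, 10.1 names adverse event incidence explicitly, and the power calculation works on the mean-difference scale that belongs to 10.1. An analyst could follow either section and claim to have followed the plan. If the choice is made after the data are seen, the nominal 5% error rate no longer holds.

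The secondary point is the interaction. In a design with two sequences and two periods, the treatment-period interaction is aliased with sequence and carryover. Once it is in the model, the coefficient labelled treatment depends on how the factors are coded. It can be the within-subject effect averaged over both periods, or the effect in one reference period, which compares 6 subjects with 6 others. Sections 10.2 and 10.3 do not say which is meant.

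**Working it through.** **Inputs.** From the plan: n = 12 and alpha 0.05 (10.4); 3 of each gender per sequence, so 6 subjects per sequence (7.3); differences of 1.5 or 2.0 events and SDs of 1.0, 1.5 or 2.0 (10.4). The documents give no adverse event rate and no within-subject correlation, so both are assumed below.

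**1. The plan's own power figures.** Two-sided paired t-test, 11 df, noncentrality d·√12/SD. For d = 1.5 and SD = 1.5 this is 1.5 × 3.464/1.5 = 3.464, which gives power 0.883. The six rows come out as 0.997, 0.883, 0.658, 1.000, 0.987 and 0.883. All match, so the table is on the difference-in-means scale.

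**2. Event means behind the table.** For independent Poisson counts, the variance of the difference is mT + mP and its mean is mT − mP. Hence mT = (SD² + d)/2 and mP = (SD² − d)/2. For d = 1.5 and SD = 2.0: mT = (4 + 1.5)/2 = 2.75 and mP = (4 − 1.5)/2 = 1.25. The two SD 1.0 rows cannot arise this way, because mT + mP would be 1.0 while mT − mP is 1.5 or 2.0. Four rows remain.

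**3. Do the two models agree?** Simulation of 100,000 trials per row, 6 subjects per sequence. Linear model: period-adjusted within-subject t-test, 10 df. Poisson model: likelihood-ratio (LR) test of the contrast averaged over periods.

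| Difference, SD | mT, mP | Different verdicts at 0.05 |
|---|---|---|
| 1.5, 2.0 | 2.75, 1.25 | 15.5% (Poisson only 12.6%, linear only 2.9%) |
| 2.0, 2.0 | 3.0, 1.0 | about 7% |
| 1.5, 1.5 | 1.875, 0.375 | about 7% |
| 2.0, 1.5 | 2.125, 0.125 | 0.3% |

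In the SD 2.0 rows a Wald test gives 15.0% and 7.6%. Without the interaction the LR figures there are 14.9% and 7.1%, so the disagreement comes from linear versus Poisson, not from the interaction.

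**4. False-positive rate if whichever model is significant is reported.** Equal assumed rates, 200,000 trials; linear rejections plus Poisson-only rejections:
- 1.0 event per subject-period: 0.049 + 0.014 = 0.063 (Wald); 0.049 + 0.030 = 0.079 (LR).
- 2.0 events: 0.049 + 0.020 = 0.069 (Wald); 0.049 + 0.024 = 0.073 (LR).

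A repeat run put the LR figure at 1.0 event at 0.080. The LR test alone has size about 0.060 there, so part of the upper figure is the test's own liberality and not the effect of choosing.

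**5. Which contrast?** On the linear scale, with total variance σ² and within-subject correlation ρ, the averaged contrast has variance 2σ²(1 − ρ)/12 = σ²(1 − ρ)/6, with or without the interaction when data are complete. The single-period contrast has variance σ²(1/6 + 1/6) = σ²/3. The ratio is 2/(1 − ρ): 2, 4 and 10 at assumed ρ of 0, 0.5 and 0.8. For Poisson counts in the 1.5, SD 2.0 row, Wald power is 0.43 for the single-period contrast, 0.73 for the averaged contrast and 0.74 without the interaction.

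**6. Limits of the Poisson model.** With the interaction, the Wald estimate is non-finite if any treatment-by-period cell is empty. The probability is 1 − (1 − e^(−6mT))²(1 − e^(−6mP))²: 64%, 18% and 1% at equal rates of 0.25, 0.5 and 1.0, against 10%, 0.5% and 0% without the interaction. If counts also vary between visits (assumed gamma heterogeneity, variance 0.5 per subject-period), the size of a Poisson Wald test with an exact fallback for empty cells is about 0.09 at a rate of 1.0 and 0.15 at 2.0. The linear model stays near 0.047.

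The Poisson calculations set the subject variance to zero. Age and sex were not simulated.

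**The case against.** The strongest reply is that 10.1 is a general overview, perhaps loosely worded for a generalized linear model, and that 10.2, which restates the primary endpoint and names its model, naturally governs. Section 10.4 calls its calculation a simplification, so it need not bind the analysis. This is a reasonable reading, and probably the intended one. But 10.1 names adverse event incidence and gives it the same linear model as the continuous scores, and a pre-specified primary analysis should not depend on a lenient reading.

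On the contrast, a reader might infer that the plan gives up the crossover's precision by including the interaction. The documents do not support that. Section 4 and the paired means of 10.4 both point to the within-subject effect, no section proposes a single-period result, and the averaged contrast loses essentially nothing. The loss in step 5 arises only if a reference-coded coefficient is reported.

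The difference between 10.1 and 10.3 is mostly elaboration: both are normal-theory mixed models, and 10.3 adds a term. It is a minor inconsistency.

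It is also fair that the percentages rest on assumed rates and independent Poisson counts, and that the planned summaries by treatment and period would show the event counts whichever model is used.

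**Conclusion.** The point holds as an ambiguity worth fixing. The contradiction between 10.1 and 10.2 is in the text and needs no simulation. Its size, under independent Poisson counts with means taken from 10.4, is a different verdict in about 0.3% to 15.5% of trials. With equal assumed rates of 1 to 2 events per subject-period, a free choice between the models gives a false-positive rate of about 6.3% to 8%. The unstated contrast is secondary.

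Three stronger readings should not be drawn. The power table is not wrong: it reproduces in every row. The calculations do not show that Poisson is the better model: with visit-level overdispersion it is anti-conservative, while the linear model kept its size. Nor does the ambiguity threaten a go/no-go decision, because the plan ties none to significance.

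**What to change.** 1. In 10.1, remove adverse event counts from the linear-model sentence and refer to 10.2, so that one pre-specified model governs the primary endpoint. Align the remaining model terms in 10.1 with 10.3.
2. In 10.2 and 10.3, add a sentence such as: the reported treatment effect is the within-subject glulisine-versus-placebo contrast, adjusted for period and averaged over both periods, with a 95% confidence interval (a rate ratio in 10.2, a mean difference in 10.3). Drop the interaction, or keep it only with this averaged contrast.

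The cost is wording in three sections; design, data and sample size do not change.

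The downside to acknowledge in the plan is that the Poisson model is anti-conservative if counts are overdispersed at visit level, and that its estimate may be non-finite if a treatment-by-period cell is empty. An exact test for empty cells is a tempting addition, but it does not come free. At assumed rates of 0.5 versus 0.1 events per subject-period, a Wald test with an exact fallback has power 0.20, against 0.48 with an LR fallback. Nor does it protect the error rate under the overdispersion in step 6. It is therefore not recommended here.
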